9.4.5 Interim Analyses

No interim analyses are planned at this time.

9.4.6 Sub-Group Analyses

We are planning the following subgroup analyses, if enough data are available. The analysis approaches are described above.

- Clinics with vs. without prior experience with DA,
- Setting, private vs. academic,
- Location, urban vs. suburban,
- Type of clinic, general rheumatology clinic vs. lupus clinic vs. rheumatology/renal hybrid clinic,
- By the language of decision-aid used English vs. Spanish,
- Patient characteristics including the biological variables (age group, sex, race/ethnicity), and
- The proportion of patients with Medicaid/Medicare vs. private insurance
- By presence of renal disease
- By level of education
- By insurance mix (>30% private)

9.4.7 Missing Data and Outliers

The rate of missing values will be evaluated on a variable-by-variable basis. Clinics and/or patients with extensive missing values will be deleted from all analyses. A clinic or patient with a missing value for any variable involved in a specific analysis will be excluded from that analysis only (case wise deletion). There are no plans for imputation of missing values. Theoretical assumptions for all statistical procedures will be evaluated (e.g., evaluation of normality, residual plots, and outlier evaluations). Any outliers will be inspected for data coding and entry errors and they will be corrected whenever appropriate. In the case of true outliers, sensitivity analyses with the specific values removed will be conducted in order to evaluate the robustness of the observed results.

In the event that there is insufficient (or excessive) variation in implementation strategies to create 2 clearly differentiable study groups, alternative definitions of the primary independent variable may be created (e.g., groups determined by number of strategies used or groups determined by percentage of staff trained).

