8 STUDY ASSESSMENTS AND PROCEDURES

This study will be coordinated by the University of Alabama at Birmingham (UAB). All study visits and procedures will be performed at the United States, and at n = 16 sites. At least 35 participants are expected to be enrolled at each site. Enrollment will be competitive between sites.

Participants will be seen according to the details that follow:

Specific Aim 1: Clinic Personnel Survey/Semi Structured Interviews

This Specific Aim will: a) identify clinic staff and patient needs, and b) key contextual factors that inform targeted strategy selected influence implementation effectiveness, and sustainability. It will do so via two data collection efforts:

Clinic Personnel Survey

Up to 15 clinic personnel will be administered an online survey via Qualtrics® to assess their role in the clinic, clinic culture, and readiness to implement change. This will last between 20-25 minutes. Clinic personnel will be emailed a link to complete the survey. An automatic email will be generated in the Qualtrics® system and will go out to all non-responders every 24 hours for 5 days, or until the survey is completed.

Semi-Structured Interviews

Each site PI/ study coordinator will choose 6-8 key clinic staff that will be administered a 45-60 minute semi-structured interview either via phone or in person that will assess stakeholder needs and identify characteristics of the clinics (e.g., policy environment, physician, clinic, patient barriers) that influence DA adoption and choice of the implementation strategy. The interview protocol will be adapted to fit each time range and different key personnel. A link to the brief video animation introducing the decision-aid use and content along with the interview protocol and copy of the decision-aid will be emailed to clinic personnel prior to being interviewed. All interviews will be recorded and transcribed verbatim for accuracy.

Specific Aim 2: Implementation

Patient Baseline Visit

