9.3 Populations for Analyses

The analysis population for each Specific Aim is below:

Specific Aim 1

- Key clinic personnel who complete the semi-structured in depth phone interview (6-8 staff per clinic)
- Clinic personnel who complete the online clinic personnel survey (all staff, up to 15 per clinic)
- Using administrative records, sites will report the total number of patients viewing the DA and the total number of patient visits during the active study time frame.

Specific Aim 2

- All enrolled participants who complete the baseline visit, as well as those who complete the three and six month follow-up questionnaires
- Clinic personnel who complete the online surveys

Specific Aim 3

- Key clinic personnel from Aim 1+ 2 patients per site who complete the post-study semi-structured in depth phone interview. (6-8 key clinic personnel + 2 patients per site)
-

The protocol population will be all participants who attend all study visits and complete the trial.

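### Section 9.4.7 removes clinics and patients with undefined *extensive* missing data from every analysis, which discards observed data, and no sensitivity analysis addresses missingness

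*Combined protocol and SAP*

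**What the plan says.** Section 9.4.7 has two exclusion rules. The first is global: "Clinics and/or patients with extensive missing values will be deleted from all analyses". The second is local: "A clinic or patient with a missing value for any variable involved in a specific analysis will be excluded from that analysis only". Missing rates are to be examined variable by variable, but no rate triggers the first rule. The section also says "There are no plans for imputation of missing values". Its one sensitivity analysis is for a different problem: "In the case of true outliers, sensitivity analyses with the specific values removed will be conducted".

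Section 9.3 defines the Aim 2 patient population as "All enrolled participants who complete the baseline visit, as well as those who complete the three and six month follow-up questionnaires", with no exclusion for missing data. It adds "The protocol population will be all participants who attend all study visits and complete the trial", but no section assigns an analysis to that population. For penetration it says "Using administrative records, sites will report the total number of patients viewing the DA and the total number of patient visits", so that outcome does not depend on survey response.

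Sections 9.1 and 9.4.2 plan GEE models for repeated measures with clinic clustering, without a working correlation, and a fuzzy-set Qualitative Comparative Analysis (fsQCA) for clinic-level outcomes.

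**The concern.** The global rule goes further than the local one. The local rule already removes a unit wherever its data are insufficient, so all that the global rule adds is removal from analyses for which the data are present.

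- **The analysis set is open.** The plan names no percentage, number of waves, list of variables, decision time or decision-maker. Two analysts could apply the sentence to the same data and keep different clinics.
- **Observed data are lost.** A clinic with sparse surveys would lose penetration counts that come from administrative records. It would also lose its patients' surveys ("At least 35 participants are expected to be enrolled at each site") and its fsQCA case. A patient with missed follow-ups would lose the baseline survey that section 9.3 admits.
- **The effect would go unseen.** Nothing planned shows how far results depend on who was removed.

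**Working it through.** **The plan's own figures.** The plan gives no figure for missing data. Its only precision figures are in section 9.2: 95% interval widths of 5.3 and 8.1 points for proportions of 10% and 40%, and 0.09 and 0.35 for Likert SDs of 0.5 and 2.0. The sample size behind them is not stated. With 16 × 35 = 560 patients and ICC 0.05, the design effect is 1 + 34 × 0.05 = 2.7, and the widths come to 8.2 and 13.3 points, and 0.136 and 0.544. Without the design effect they are 5.0 and 8.1 points, and 0.083 and 0.331. The stated set is not reproduced. That is a separate matter, and the relative figures below do not depend on it.

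**Precision lost when clinics are deleted.** With k equal clinics of m patients, width = 2 × 1.96 × SD × √([1 + (m − 1) × ICC] / (k × m)). With m fixed, width is proportional to 1/√k.

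- 2 clinics lost: √(16/14) = 1.069, about 7% wider.
- 4 clinics lost: √(16/12) = 1.155, about 15% wider.
- Example, Likert SD 0.5, m = 35, ICC 0.05: 0.136 becomes 0.145 or 0.157.
- fsQCA: each clinic is 1/16 = 6.25% of the cases.

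**Patients deleted.** Suppose *extensive* means both follow-ups missed, with independent response r at each (an assumption). Deletions among 560 are 560 × (1 − r)²: about 6, 22 or 50 at r = 90%, 80% or 70%. Each has an observed baseline survey that would be discarded.

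**Direction of any bias.** This was simulated with assumed inputs: 1,000,000 patients, three waves, SD 1, within-patient correlation 0.5, true change 0, 20% missing at each follow-up, no clinic clustering. Entries are the estimated 6-month change in SD units.

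| Low scorers more often missing, according to | Working correlation | All waves kept | Both-missed deleted | Completers only |
|---|---|---|---|---|
| Baseline score | Exchangeable 0.5 | 0.00 | −0.02 | −0.09 |
| Baseline score | Independence | +0.05 | +0.01 | −0.09 |
| Current score | Exchangeable 0.5 | +0.07 | not needed here | +0.05 |

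Signs reverse if high scorers are the ones missing. In the first row deletion creates a small error; in the second it reduces one. Completers-only is the worst estimator in both. In the third row it errs in the same direction as the all-waves model, so agreement between the two would reassure falsely.

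**The case against.** The strongest reply is that the rule may rarely apply and do little when it does. The plan works to limit missing data: reminders and mailed surveys (section 5.8), a survey at the next visit for non-responders (section 8), missing-data queries to sites (section 10.1.7) and window tracking every two weeks (section 10.5). Sections 7.1 and 7.2 document withdrawal reasons and contact attempts. If *extensive* means both follow-ups missed, the simulated error is −0.02 SD or smaller. The interval for a 6-month change with 448 pairs (80% of 560) is about 2 × 1.96 × 1/√448 = 0.19 wide before clustering. All of that stands and lowers the stakes. None of it defines the rule, limits it or tests its effect.

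A reader might infer that one missed survey deletes a patient. On that reading 106, 202 or 286 of 560 patients would go at 90%, 80% or 70% response, from 560 × (1 − r²). The documents work against it. The local rule sends an isolated gap to exclusion from one analysis. Section 9.3 admits baseline completers. Section 10.5 expects some patients to miss month 3 permanently and still complete month 6. It remains worth stating that a missed wave costs only that wave, but as a clarification.

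A reader might also infer that deletion would flatter the results, because clinics with poor data are the clinics with poor uptake. The documents give no link between missingness and performance, so this cannot be claimed.

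**Conclusion.** The point holds as a fault in the rule, not as a demonstrated bias. The rule is undefined, reaches analyses for which the data exist, conflicts with the section 9.3 population and has no sensitivity analysis behind it. The demonstrable cost is precision: intervals about 7% or 15% wider if 2 or 4 of 16 clinics are removed, assuming equal clinic sizes and needing no assumption about why data are missing. Bias could be nil, positive or negative. The simulated values illustrate that under assumed response rates and correlations; they do not predict this study. The point should be settled before the analysis data are examined, since the main risk is a decision made with the results in view.

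**What to change.** 1. Delete the global removal sentence in section 9.4.7 and keep the analysis-specific rule. Each clinic and patient then stays in every analysis for which the needed data exist. A clinic leaves fsQCA only if a condition or the outcome cannot be scored, and it is listed.
2. State that a missed wave removes that wave and not the patient. Fit the longitudinal model to all available waves with a pre-stated within-patient correlation other than independence, or use an equivalent mixed model.
3. Add one missing-data sensitivity analysis: multiple imputation, or inverse-probability-weighted GEE, using baseline score and clinic. Do not use completers-only for this purpose, for the reasons in the table. If imputation is chosen, the sentence ruling it out must change; weighting leaves it intact. Neither method corrects for missingness that depends on the unobserved score itself, and the report should say so.
4. Report response by clinic and wave.

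The cost is SAP wording and a small amount of programming. No new data are needed, and study conduct does not change.

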6.3 Implementation Strategy Fidelity and Adaptation

Study investigators will develop and work with clinic personnel to apply the standardized and tailored implementation activities within the clinic setting. It is expected that strategies will be adapted to suit each clinic's unique context and circumstances. We therefore expect to implement 16 different approaches. We will capture and describe each unique approach and use these findings to inform key outcomes. The periodic check-ins for each site following the Education, Training, and Refresher Training standardized activities will allow study personnel to determine the extent to which the DA has been implemented within clinic flow and processes.

Patient participant study compliance will be measured by completion of all study assessments, including the three and six month follow-up and semi-structured in-depth phone interviews. We will also assess whether or not the patient views the DA at the first visit at baseline and/or requests an electronic or paper copy of the DA (Aim 2).

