the alternative that there is a change over time. For the analytic approach we will examine mean levels (total change) and quantify with means (or proportions, as appropriate) and 95% confidence intervals. We will also examine patterns of change (growth trajectories) while controlling for differences between clinics using multivariable models that account for repeated measures and clinic clustering of patients (i.e., generalized estimating equations (GEE) with robust standard errors). Additional analyses may examine by-group comparisons of clinics determined by clinical characteristics (e.g., geographic areas, clinic type, and patient diversity) observed in Specific Aim 1. Any such by-group analyses will be conducted separately. A primary independent variable of interest is the type of strategy used for implementation. Following completion of the study, each sites strategies will be evaluated and sites will be grouped accordingly. A covariate allowing for testing group differences will be included in the multivariable models to assess whether trajectories differ by implementation strategy.

The second component of our evaluation of Specific Aim 2 will use fuzzy set Qualitative Comparative Analysis (fsQCA) to assess effectiveness of implementation strategies for clinic-level outcomes. fsQCA is a case-oriented approach that examines relationships between conditions (similar to explanatory variables in regression models) and outcomes using set theory to answer the question: “what conditions, alone or in combination, are necessary or sufficient to produce an outcome?” For patient-physician communication analysis, question-asking, assertive responses, and expressions of concern, will be coded as patient participation; supportive talk and partnership building by provider will be coded as active physician communication. Further details are provided in Section 9.4.

Specific Aim 3: Targeted participants for this Specific Aim are the same key clinic informants from Specific Aim 1 and 2 patients per clinic from Specific Aim 2. Similar to Specific Aim 1, the analytic approach is largely descriptive and there are no formal statistical null and alternative hypotheses. Specific descriptive statistics are described in the table below. Further details are provided in Section 9.4.

Specific Aim 3 Data Collection and Analyses		
Data Type	Interview Content	Analytic Methods

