9.2 Sample Size Determination

A power analysis for the quantitative portion of Specific Aim 2 was conducted using the following assumptions: (1) 16 clinics and (2) an intraclass correlation coefficient of 0.05. This provided us with a total confidence interval width of 5.3% for 10% of the total clinic population that is administered the lupus DA to a width of 8.1% , if 40% patients are administered the lupus DA. For outcomes on a 5-point Likert scale, the corresponding 95% CI widths for standard deviation of 0.5 and 2.0 on the mean score is estimated to be 0.09 vs. 0.35, respectively. For individual-level outcomes measured as a rate (e.g., # visits/1,000) or as means (e.g., Likert-scale), we anticipate small margins of error. A minimum number of proposed sites (n=16) are needed to comprehensively assess how different implementation strategies are influenced by and interact with different contextual conditions (different geographic areas, clinic type, and patient diversity) to affect implementation effectiveness, and thus, determine the generalizability of the study findings. However, given the proven effectiveness of the DA (original PCORI study), and in the spirit of dissemination and implementation research, we will continue to recruit to our proposed maximum sample size target of 3,000.

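### The fallback strategy variable in 9.4.7 groups two numeric clinic measures; if the relation is roughly linear, a two-group cut of 16 clinics loses power, and no numeric form or cut-point is specified

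*Combined protocol and SAP*

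**What the plan says.** Section 9.1 (Specific Aim 2) states: "A primary independent variable of interest is the type of strategy used for implementation". It continues: "Following completion of the study, each sites strategies will be evaluated and sites will be grouped accordingly". It then adds: "A covariate allowing for testing group differences will be included in the multivariable models", so the variable enters the GEE as a grouping.

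Section 9.4.7 covers the case where there is "insufficient (or excessive) variation in implementation strategies to create 2 clearly differentiable study groups". Alternative definitions may then be created, and the two examples given are "groups determined by number of strategies used or groups determined by percentage of staff trained". The section does not say where the cuts would fall or how many groups the alternatives would have. No section provides for using the count or the percentage as a number.

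Section 6.1 lists seven tailored activities, three clinic-targeted and four patient-targeted, and sites may use either kind or both. Section 6.3 says of the adapted strategies: "We therefore expect to implement 16 different approaches".

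**The concern.** Strategy varies only between clinics, so a strategy effect is estimated from 16 units however many patients are enrolled. Cutting a numeric clinic measure into groups discards the order and spacing of clinics within each group. The planned GEE does not require this, since a numeric covariate fits the same model. If more implementation effort goes with better outcomes in a graded way, the grouped test is more likely to miss it, and the trial would report no difference by strategy.

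The open cut-point adds to this. Grouping follows study completion, and nothing states that the cut is fixed before outcomes are seen.

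**Working it through.** **Inputs from the documents.** Section 9.2 assumes "1) 16 clinics and (2) an intraclass correlation coefficient of 0.05". Section 8 says: "At least 35 participants are expected to be enrolled at each site". Significance is at 0.05 (section 9.4.4, in the baseline descriptive text; two-sided is assumed here).

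**Assumed, because the documents are silent.** Effect size, distribution of each measure, cut-point, shape of the relation, and equal clinic sizes.

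**Plan's own figure.** There is none to reproduce. The confidence-interval widths in section 9.2 concern overall proportions and means, not the strategy comparison, for which no power is stated.

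**Step 1: scale.** With patient SD 1, the clinic-mean variance is 0.05 + 0.95/35 = 0.0771, so its SD is 0.278. An effect b of 0.3 to 1.0 clinic-mean SD per SD of the measure is 0.3 × 0.278 = 0.08 to 1.0 × 0.278 = 0.28 patient SD. The clinic-level correlation is b/√(1+b²), that is 0.29 to 0.71.

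**Step 2: rough size.** A median split of a normal measure correlates √(2/π) = 0.80 with the measure itself, so it keeps 2/π = 64% of the information: 0.64 × 16 ≈ 10 clinics' worth. For a uniform measure the share is 0.75, or 12 clinics' worth.

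**Step 3: simulation under a linear relation.** Clinic value = b·x + N(0,1) in clinic-mean SD units, 16 clinics, 60,000 replicates per cell. The numeric analysis is the slope t test on 14 df. The grouped analysis is the two-sample t test after an 8:8 median split, with ties in the count broken at random. Power in %, numeric vs split (loss in points):

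| b | Normal | Uniform | Count, Binomial(7, 0.5) |
|---|---|---|---|
| 0.3 | 19 vs 13 (6) | 19 vs 15 (5) | 19 vs 13 (6) |
| 0.5 | 43 vs 27 (16) | 43 vs 31 (12) | 43 vs 26 (17) |
| 0.6 | 56 vs 35 (20) | 57 vs 41 (16) | 56 vs 35 (22) |
| 0.8 | 78 vs 53 (25) | 80 vs 61 (20) | 78 vs 51 (27) |
| 1.0 | 91 vs 68 (23) | 93 vs 76 (16) | 91 vs 66 (25) |

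Losses are taken before rounding. Both t tests hold about 5% at b = 0. The unit is the SD of the clinic value, so the comparison carries over to clinic-level change scores. The loss fades for very strong effects: 2 points at correlation 0.9 (normal measure).

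**Step 4: other cuts and shapes.**
- A 12:4 cut of these three measures loses about 7 to 37 points over the same effects.
- Three ordered groups scored as a trend lose about 2 to 15.
- A skewed (exponential) measure with a median split loses about 9 to 33 over correlations 0.3 to 0.8. For such a measure an uneven cut can lose less than a median split.
- If the truth is a step exactly at the cut (correlation 0.6 with the step), the numeric term has 52% power and the split 80%. If the step is at the population median but the cut is at the sample median, the figures are 52% and 55%.

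**Step 5: the planned test.** With equal clinic sizes, a clinic-level term in the GEE reduces to a regression on clinic values with a sandwich variance. At b = 0, the uncorrected robust Wald test (1.96 reference) rejects about 9% of the time for the 8:8 split. For the numeric term it rejects about 11% (uniform), 13% (count) and 13 to 14% (normal). A Mancl-DeRouen correction with a t reference on 14 df brings this to 4.5 to 5.1% (numeric) and about 3.7% (split). The milder Kauermann-Carroll correction leaves 6.5 to 7.4% for the numeric term. Under the Mancl-DeRouen test the loss from splitting is still about 5 to 25 points.

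**The case against.** The strongest case against has four parts.

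**The text is permissive.** It says alternatives may be created and gives examples, so a numeric definition is not excluded. This stands: it is a contingency left open, not a fixed rule with a known cost.

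**The fallback may never be used.** A reader might infer from the 16 expected approaches in section 6.3 that excessive variation is foreseen and the fallback is the likely analysis. The documents do not support that. Section 6.3 describes adaptation to local context, and section 6.1 supplies a ready grouping: clinic-targeted, patient-targeted, or both.

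**The size and even the sign depend on unstated facts.** This stands. No single loss figure is a property of this plan, and a step at the cut reverses the comparison. A numeric term also has its own weaknesses. Section 6.1 has all clinic personnel trained by video, so percentage trained may cluster near 100% and leave the slope resting on a few clinics. A count treats a poster and audit-and-feedback as equal.

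**A numeric term can worsen false positives in the planned model.** This also stands. That both methods hold 5% is true of t tests on clinic values, not of uncorrected robust standard errors with 16 clusters.

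The consequence is also bounded. The stated Aim 2 null is no change over time, and section 9.1 also assesses strategies by fuzzy-set QCA, which allows graded membership. None of this removes the gap: the only forms named are grouped, with no cut-point.

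**Conclusion.** The concern holds as a gap in a conditional fallback. Given a roughly linear relation, cutting the count or percentage at the median across 16 clinics costs about 5 to 27 points of power for assumed effects of 0.3 to 1.0 clinic-mean SD per SD of the measure. Uneven cuts of a symmetric measure cost more, and three ordered groups less. These figures rest on assumed effect sizes, distributions and equal clinic sizes.

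Two stronger readings are not supported. One is that numeric is always better, which fails under a step relation. The other is that the cut would be chosen to suit the results: the plan says only that grouping follows completion, without saying whether outcomes will have been seen.

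**What to change.** In section 9.4.7, state that if the fallback is used:

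- The number of tailored strategies enters the model as a numeric clinic-level covariate with its interaction with time. Percentage of staff trained may be used instead if it varies enough between clinics. That choice is made from implementation records before outcomes are seen.
- The term is tested with a small-sample correction for 16 clusters, such as Mancl-DeRouen bias-corrected sandwich standard errors with a t reference.
- Linearity is checked by plotting the 16 clinic values.
- A grouped analysis, with its cut fixed before outcomes are seen, is kept as a sensitivity analysis.

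The cost is a few sentences and a little more analysis work, with no new data. The downside is reliance on approximate linearity, which the plot and the grouped sensitivity analysis address.
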